4.1. Treatment Design

The intervention and its compliance criteria are defined as receiving treatment by minimum 72 hours since loading dose start time or up to ten complete days with administration of two of the following ASM regimens:

Phenobarbital:

Pediatric population

Loading dose 20 mg/kg intravenous. Max dose 1000mg
Maintenance dose 4mg/kg/day. Max dose 300mg/day.

Adult population

Loading dose 20 mg/kg intravenous.
Maintenance dose 4mg/kg/day. Max dose 600mg/day.

Levetiracetam

Pediatric population

Loading dose 60 mg/kg intravenous. Max dose 4000mg.
Maintenance dose 40mg/Kg/day, Max dose 3000mg/day intravenous or enteral.

Adult population

Loading dose 60 mg/kg intravenous. Max dose 4500mg.
Maintenance dose 1500mg to 4000mg/day intravenous or enteral.

Lacosamide

Pediatric population

Loading dose 10 mg/kg intravenous, Max dose 400mg.
Maintenance dose 4mg to 8mg/Kg/day. Max dose 300mg intravenous or enteral.

Adult population

Loading dose 200mg to 400mg intravenous
Maintenance dose 200-400mg/day intravenous or enteral.

Valproate

Pediatric population

Loading dose 30mg/kg intravenous. Max dose 3000mg
Maintenance dose 20mg to 30mg/Kg/day, Max dose 3000mg/day.

Adult population

Loading dose 40 mg/kg intravenous. Max dose 3000mg
Maintenance dose 15-30mg/Kg/day, Max dose 3000mg/day.

Phosphenytoin,

Pediatric population

Loading dose 20 mg PE/kg intravenous. Max dose 1500mg PE
Maintenance dose 4mg PE/Kg/day. Max dose 300mg PE/day.

Adult population

Loading dose 20 mg/kg intravenous. Max dose 1500mg PE
Maintenance dose 4-7mg PE/Kg/day. Max dose 400mg PE/day

All maintenance doses are given every 12 hours, starting 12 hours after the loading dose.

Participants with GCS 9 to 12 will not receive phenobarbital as one of the intervention ASM, and the loading dose of one of the two selected ASMs will be omitted.

All patients with an identified SzNET in rs-fMRI#1 will be included in the intervention group. Within one and six days after the first scan, the care team will decide and start the intervention with two ASM agents from the list. The intervention phase occurs between rs-fMRI#1 and the day of follow-up rs-fMRI#2 and repeated EEG. The intervention is considered complete and the follow-up tests can be done if the patient received the study ASM for at least 72 hours after the loading dose start, and the second scan must be done within 72 hours of the last intervention ASM dose. The treatment protocol can continue up to a maximum of ten days to improve the opportunity to schedule the scan. Thus, the rs-fMRI #2 must be done at a time between 73h and 312h (the fourth and thirteenth days) after the intervention phase starts, and the subject can still be receiving the intervention at that time.

Once the rs-fMRI #2 is obtained, the subject's ASM treatment can be continued or changed for clinical reasons depending entirely on the care team's decision, then it will not be considered part of the study's intervention phase or be related to the research team.

The intervention aims to validate the epileptogenic background of the SzNET by using an ASM that is known to be effective. We expect the intervention will influence the improvement of the SzNET. We hypothesize that the intervention will selectively modulate the networks caused by epileptogenic activity, while having less to no impact on abnormal networks caused by other phenomena.

The length of the intervention is designed to be adequate for pharmacological modulation of epileptogenic activity. The six-day time frame between the minimum and the maximum treatment protocol time facilitates a window for the rs-fMRI schedule that is a realistic schedule time frame in the ICU.

From the different ASM options the key intervention and first option to be considered as intervention will be phenobarbital + levetiracetam. This specific ASM combination will be communicated clearly to the ICU care teams as the first line of the study intervention. However, for clinical reasons the care team will be free to select any combination of two or more study listed ASM regimens. On day two of maintenance dosing, the phenobarbital serum level will be measured if it is one of the selected medications, and a new loading dose will be given to aim for a level of 40mcg/ml.

The dual ASM loading dose approach is designed to increase the likelihood of a timely response to SzNET, as compared to using only one ASM and its rational use is supported by the better response suggested in Status epilepticus^{23,24}. With a gentler medication regimen of single agent, given the data, should be less likely to see an impact on the SzNET. If we go this route and we don't see an effect, then we are also unlikely to get any further funding to repeat such a study with dual agent, given the competitive nature of grant application and the clinical team may also loose appetite for supporting more studies.

Phenobarbital is included specifically because of its high efficacy in treating epileptogenic activity^{25,26}. Phenobarbital can cause ventilatory depression. However, the patients with SABI during the study timeframe are expected to be intubated with good airway and ventilatory control, and thus less likely to require significant escalation of airway or ventilatory support. Furthermore, all ICU patients are monitored with all necessary safety considerations for airway management and ventilation. ASM maintenance dosing can be modified by the care team during the intervention phase and still be compliant, as long as the dose remain equal or higher than the minimum dosage stated in the insert. The care team may adjust ASM based on clinical determinants after the second rs-fMRI without compromising the protocol, as the main outcome measures are based on data collected on that day.

The short term-use of dual ASM that we would be giving to patients with suspected non-convulsive status epilepticus or subclinical seizures with coma in the ICU is off-label because the intervention is not given to treat confirmed seizures by their standard definition. However, the possibility of deleterious epileptogenic activity cannot be discarded in the eligible patients and the routes of administration and concomitant dosage levels are appropriate for status epilepticus (see appendix B to F), not increasing the risk of the intervention compare to the regular use of the listed ASM. The study's intervention does not significantly increase the selected subjects' risks leading to a discouraging risk-benefit relationship because these subjects are already at very high risk of death if they do not wake up from their coma. Thus, any opportunity to try to improve the chances of waking up from coma is worth

the risk of the antiseizure medication. That risk benefit relationship is the reason why empiric antiseizure medication is often given in SABI patients with DoC.

Participants with a GCS of 9 to 12 are at lower risk compared to those with a GCS of less than 9 and may not require ventilatory support. To maintain a favorable risk-benefit ratio for their participation, these participants will not receive phenobarbital as one of the intervention ASM, and the loading dose of one of the two selected ASMs will be omitted.

The present study and its results are not intended to try to support changes in the indications, the labeling or the advertising of medical devices use or drugs. The study's informed consent will describe the purpose and the procedures and interventions described in this trial. Taking into account the statements in this protocol we are not submitting an FDA " Investigational New drug Application (IND)" because according to 21 CFR 312.2(b)(1), the clinical investigation of a marketed drug or biologic does not require submission of an IND if all six of the following conditions are met:

- i. it is not intended to be reported to FDA in support of a new indication for use or to support any other significant change in the labeling for the drug;
- ii. it is not intended to support a significant change in the advertising for the product;
- iii. it does not involve a route of administration or dosage level, use in a subject population, or other factor that significantly increases the risks (or decreases the acceptability of the risks) associated with the use of the drug product;
- iv. it is conducted in compliance with the requirements for IRB review and informed consent [21 CFR parts 56 and 50, respectively]; (revision by the IRB and compliance with the protection of human subjects)
- v. it is conducted in compliance with the requirements concerning the promotion and sale of drugs [21 CFR 312.7]; and
- vi. it does not intend to invoke 21 CFR 50.24.²⁹

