The study's main intervention option consists of the Phenobarbital and Levetiracetam regimens. However, the clinical team can select any combination of two or more ASM regimens from the list provided, for clinical reasons. On day two of intervention, the phenobarbital serum level will be measured if it was one of the selected medications, and a new loading dose will be given to aim for a serum level of 40mcg/ml.

Participants with GCS 9 to 12 will not receive phenobarbital as one of the intervention anti-seizure medications (ASM), and the loading dose of one of the two selected ASMs will be omitted. For these participants the study's main intervention option consists of the Levetiracetam and Lacosamide regimens, omitting the Lacosamide loading dose.

Rs-fMRI schedule (Day 0-1 of Enrollment)

- Order Pre-Intervention research-related rs-fMRI#1

Time from enrollment to intervention start (Days 1-6 of Enrollment)

- Scan **should** be performed within 3 days **from enrollment**.
- **To undergo any study indicated rs-fMRI, the participant should not have been diagnosed with vasospasm based on their most recent transcranial Doppler examination, conducted within the last 3 days.**
- The time frame between fMRI scan and intervention start will range from 1 to 6 days.
- Obtain (research driven) fMRI
 - What is rs-fMRI
 - ♦ MRI generates images based on the interaction of the body with potent electromagnetic fields.
 - ♦ Rs-fMRI uses BOLD signal to identify vascular reflexes related to neuronal activation.

- What is the process of transporting the patient to the fMRI?
 - ◆ As SOC at UNC Health, a transport team made of two nurses, one fellow physician and one respiratory therapist gathers with the patients at ICU and checks to have the required equipment for transportation.
 - ◆ The subject is transported by the transport team from the ICU to the MRI Scan within the hospital, located on the first floor or the basement of the same ICU building, according to the MRI scanner availability.
 - ◆ Once the rs-fMRI scanning is acquired the transport team transports the subject back to the ICU.
- How long does the fMRI routinely last?
 - ◆ Around 25 minutes for the scanning
 - ◆ Variable transportation times, from ICU to scanner and from scanner to ICU
- What are the risks associated with the fMRI?
 - ◆ Patients meeting eligibility criteria do not have risk of adverse events related to the electromagnetic fields

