 - Review adverse events
 - Review participant medical record to confirm which combined ASM was decided by the clinical care team and charge it into EPIC.
 - Document date and time of first intervention-related loading dose infusions.

Maintenance Dose (Up to 3 to 10 Days from loading dose start)

- **Research Team** will charge to EPIC the maintenance doses and verify ASM Administration.
 - The maintenance protocols must be administered for at least 72 hours from the start time of the loading dose infusion.
 - The MD can continue for up to 10 days while the second fMRI is trying to be scheduled and obtained.
 - The ASM can be continued beyond 10 days but would no longer be considered in the protocol-driven intervention phase.
 - The Post-Intervention assessment scans can be obtained, even if the participant remains on ASM beyond the maintenance dose period.
 - **To undergo any study indicated rs-fMRI, the participant should not have been diagnosed with vasospasm based on their most recent transcranial Doppler examination, conducted within the last 3 days.**
 - If one of the combined doses administered is phenobarbital
 - *On Day 2 of the MD:*
 - ♦ Specimen Collection (phenobarbital serum level UNC Hospitals Test ID LAB30) will be ordered by the research team.
 - ♦ The **research team** reconvenes the maintenance dosing with the **medical care team** to aim for a level of 40mcg/ml.
 - Review any AEs associated with ASM
 - Review Dropout data (if applicable)

- **Medical Care Team** will decide if the patient continues with the study's antiseizure medication regimens. In this case, they will continue to provide the medication, and the patient will be responsible for expenses.

Acquisition, storage and preparation: The present study does not employ experimental compounds, all the medications related to the study follow the same standard Storage rules of the medications regularly used at the ICUs of UNCH.

Administration: IV and enteral administration with infusion times and observation according to the internal protocols for each medication at the patient's corresponding ICU.

Rescue Procedures/Medications

- If emergent adjustments to the treatment plan are needed those will be decided by the care team.
- Administration of additional ASM to the study intervention is allowed as determined by the clinical team.

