Adherence Monitoring/Evaluations the intervention's ASM timing and dosing will be checked from the medical charts. On day two, the phenobarbital serum level will be measured if it was one of the selected medications, and a new loading dose will be given to aim for a serum level of 40mcg/ml.

Concomitant Therapies There are no prohibited or recommended concomitant therapies. Calcium channel blockers must be used with precaution when administering some of the protocol ASM (see appendix B & E).

Follow-up tests (Days 3-13 from Start of Loading Dose)

- Order Post-Intervention research-related rs-fMRI (#2)
 - Scan must be **performed** after completing a minimum of 72h of intervention ASM protocol (including loading and maintenance doses).
 - Scan must be **completed** within 72hrs of last intervention ASM dose.
 - **To undergo any study indicated rs-fMRI, the participant should not have been diagnosed with vasospasm based on their most recent transcranial Doppler examination, conducted within the last 3 days.**
 - Post scan, the participant can continue on their current ASM regimen or be changed based on routine clinical care decisions.
 - The official results report will be uploaded to EPIC after the post-intervention research-related EEG has been reported.
 - AE Review:
 - Review Dropout data (if applicable)
 - Collect GCS Score
- Obtain Post-Intervention research-related EEG
 - EEG characteristics
 - The EEG is a non-invasive medical test with very low risk of adverse events. Very rare complications could be associated with skin reactions to the conducting material used for the electrodes and malfunction of the device.
 - Bedside monitoring.
 - Minimum 1 hour run.
 - Without Photostimulation.
 - EEG recording must be obtained within 72hrs of last intervention ASM dose.
 - Post the EEG, the participant can continue on their current ASM regimen or be changed based on routine clinical care decisions.
 - EEG will be reviewed by a blinded epileptologist for rs-fMRI (#2) results.
 - For ethical reasons the results will be shared with the care team.

7. Schedule of Activities and Procedures

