11.3. Record Keeping and Monitoring

The results will be informed and kept as regular tests done for clinical purposes. The results will not be stored by the research team, but will be used for safety purposes to provide a one time feedback to the care team in order to adjust dosing if deemed necessary.

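### The protocol gives conflicting instructions on what follows the phenobarbital serum level, and counts the day-2 sample from different starts

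*Combined protocol and SAP*

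**What the plan says.** Six places in the current protocol deal with the level.

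- Section 4.1: "On day two of maintenance dosing, the phenobarbital serum level will be measured if it is one of the selected medications", and then "a new loading dose will be given to aim for a level of 40mcg/ml".
- Section 6, the paragraph on the main intervention option: "On day two of intervention, the phenobarbital serum level will be measured if it was one of the selected medications", and then "a new loading dose will be given to aim for a serum level of 40mcg/ml".
- Section 6, Maintenance Dose list: the sample is ordered "On Day 2 of the MD". The research team then "reconvenes the maintenance dosing with the" care team, aiming for the same 40 mcg/ml. No loading dose is mentioned.
- Section 6, Adherence Monitoring: "On day two, the phenobarbital serum level will be measured if it was one of the selected medications, and a new loading dose" is to follow, with the same target and no start named for the day count.
- Section 11.1: the sample is taken on day 2 of maintenance and is used for adjusting the dose toward 40 mcg/ml. It does not say whether a loading or a maintenance dose is meant.
- Section 11.3: the result serves to "provide a one time feedback to the care team in order to adjust dosing if deemed necessary".

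On the start of maintenance, Section 4.1 has 12-hourly dosing beginning 12 hours after the loading dose. The opening description in Section 6 has it beginning the day after.

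**The concern.** A further loading dose, a joint review of maintenance dosing, and feedback acted on only if judged necessary are three different instructions following the same laboratory result. Section 6 contains two of them, so it disagrees with itself as well as with other sections. A team working from the Maintenance Dose list would not know that a repeat load was intended. A team working from Section 4.1 would find no statement of when the repeat load is withheld or how large it is.

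The bearing on safety comes first. Phenobarbital with levetiracetam is the first-option regimen, and Section 4.1 names ventilatory depression as a phenobarbital risk. Section 12.1 sets that risk aside on the ground that recipients require ventilatory support. Section 4.1 says only that intubation is expected, and Section 5.2.1 does not make it an entry criterion.

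A secondary point concerns Aim 1. The level is sampled shortly before the second scan may take place, and Sections 11.3 and 13.4 say that levels are not kept as research data. The analysis could not show which instruction had been followed from the levels themselves.

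**Working it through.** The plan gives no derived figure to reproduce, so the check is a comparison of texts followed by arithmetic on the day count.

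**Step 1: the action and the clock in each place.**

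| Place | Action after the level | Condition stated | Day 2 counted from |
|---|---|---|---|
| 4.1 | New loading dose | None | Maintenance |
| 6, main option paragraph | New loading dose | None | Intervention |
| 6, Maintenance Dose list | Teams revisit maintenance dosing | None | Maintenance |
| 6, Adherence Monitoring | New loading dose | None | Not named |
| 11.1 | Adjust dose, type not stated | None | Maintenance |
| 11.3 | Feedback, adjust dosing | If judged necessary | Not given |

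The target is 40 mcg/ml wherever one is given. The differences lie in the action, its condition and the clock.

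**Step 2: the timing difference.** Assume that time 0 is the start of the loading dose and that a day is 24 hours.

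- Day two of intervention: 24 to 48 h.
- Day two of maintenance, with maintenance starting at 12 h (4.1): 12 + 24 = 36 h to 12 + 48 = 60 h.
- Difference: 36 − 24 = 12 h.
- Day two of maintenance, with maintenance starting the next day (6): the loading day is calendar day 1, so maintenance day 1 is calendar day 2 and maintenance day 2 is calendar day 3. Day two of intervention is calendar day 2.
- Difference: one calendar day.

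The sampling time can therefore differ by about 12 hours to one day. The minimum treatment period is 72 h from the start of loading, and Section 4.1 allows the second scan from 73 h.

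**Step 3: who is affected and by how much.** Entry requires GCS below 13, and phenobarbital is not given at GCS 9 to 12, so the issue concerns participants with GCS below 9 who are given phenobarbital. Section 5.1 expects 22 treated participants. The documents do not say how many will receive phenobarbital, so the number could be anything from 0 to 22. The only phenobarbital load defined is 20 mg/kg, and the size of a repeat load is not stated. If it is assumed equal to the first, the readings differ by up to one loading dose of 20 mg/kg. If it is sized to the measured level, the difference is not determined by the documents.

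**The case against.** The strongest reply is that the sections describe one target-guided process. A level is measured, a target is named, and a load is given to reach it. Section 11.1 supplies the purpose and Section 11.3 the condition, so 11.3 qualifies 4.1 rather than contradicting it. The amendment log records the repeat load as a change to Sections 4 and 6 only, which may explain wording elsewhere that does not mention it.

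Part of this stands. A reader might infer that 4.1 orders a second load whatever the level turns out to be. The documents do not force that reading, because aiming for a level can imply that the result guides the decision. What can be said is that no condition is written beside the instruction. The reply still does not account for the Maintenance Dose list in Section 6, which pursues the same target by a different action.

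The safeguards also count: phenobarbital is withheld at GCS 9 to 12, ICU monitoring is continuous, and the care team decides emergent changes. They limit the risk but do not say which instruction applies.

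On timing, a load given in the afternoon or evening makes 12 hours later and the next day coincide, so the two maintenance starts will sometimes agree. A reader might also infer that the sample could precede any phenobarbital, since Section 4.1 opens the intervention phase at the first scan and drug starts one to six days later. That is strained: Sections 4.1 and 6 define the intervention as receiving the drugs, and the sample applies only when phenobarbital has been selected.

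**Conclusion.** The inconsistency is real and present in the current text. Three places call for a new loading dose with no condition or size, one calls for a review of maintenance dosing, one leaves the type of dose open, and one makes adjustment optional. The day-2 clock has two named starts and one unnamed, and maintenance has two start times. The resulting timing difference of about 12 hours to one day rests on taking the loading dose as time 0.

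Two stronger conclusions are not supported. A full 20 mg/kg difference for every phenobarbital recipient would require both an unconditional repeat and a repeat equal to the first load, and the documents state neither. Nor do they support saying that the Aim 1 estimate is undermined by this wording. The protocol already permits any two or more of five drugs, 72 hours to ten days of treatment, changes to maintenance dosing, substitution of listed drugs and additional antiseizure drugs. Against that variation the added inconsistency is small. The reason to correct the text is participant safety and uniform conduct.

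**What to change.** Reconcile Section 4.1, the three places in Section 6 (main option paragraph, Maintenance Dose list, Adherence Monitoring), Section 11.1 and Section 11.3, so that all carry the same three elements: the action that follows the level, the condition under which it is taken, and the event from which day 2 is counted. If the reconciled text keeps a repeat load, its size should be stated or the basis for it given. Align Section 4.1 and the opening of Section 6 on when maintenance begins, since the sampling day depends on it. Which action, condition or timing is right is a clinical decision for the investigators, and none is proposed here.

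The cost is a wording amendment with the IRB review that the Statement of Compliance requires for any amendment. Sample size, outcomes and analysis are unaffected.
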